Final follow-up assessments, as described above in Visit 2, will be completed after 6 weeks of the tDCS intervention.

At the end of visit 18, we will provide the opportunity for participants to continue tracking their FitBit information for up to additional 3 months. If the participant agrees, we will keep the tracking option available for the study team to track the retention of the intervention. The study team will terminate this tracking service by the end of the retention phase.

Materials for recruitment and study conduct

StimFit_Recruitment_Flier_20200108_clean.pptx

StimFit_Recruitment_Flier_notabs_20200108_clean.pptx

StimFit_Recruitment_letter_20200205_tracked IRB edits_clean.doc

Assessment of Protocol Understanding Form.docx

International Physical activity Questionnaire IPAQ short procedure Q by Q and questions.docx

MOCA.pdf

Stim-Fit_Phone_Screen_2020205_clean.docx

Stim-Fit_tDCS_Eligibility_Questionnaire.docx

The PAR Q.docx

gradCPT Instructions_FrailAdults.docx

N-Back_Instruction.docx

TRAILS_V1.pdf

TRAILS_V2.pdf

Trails_v3_corrected.docx
Digit Span.pdf
Blood Pressure Form_42219.docx
DT Balance Assessment 42219.docx
DT familiarization and sitting assessment 42219.docx
DT gait assessment 42219_AlipgEdit.docx
GDS15.pdf
Height and Weight Form 42219.docx
Medical History Questionnaire_1 71318.docx
Medication Review Form_1 42219.docx
Sociodemographic Form 42219.docx
TUG form 42219.doc
BARSE.pdf
ESES worksheet_exercise_self-efficacy_scale_eses_0.docx
SEW_DUR.pdf
SRQ-Exercise_short.pdf
WHAS Pain Questions.docx
tDCS Blinding Efficacy.docx
tDCS Side Effects Questionnaire.docx
Cognitive Reserve Questionnaire.pdf

Data Analysis and Data Monitoring

Data Analysis

This study will enroll 32 participants. We have conservatively planned for approximately 20% attrition and have thus based our statistical plan on complete datasets of $n = 26$.

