Assessment of feasibility endpoints will be based on sample computations, including the screened to enrolled ratio, retention rate, assurance of blinding, and safety assessment (see above). Adverse events (AE) will be organized according to the MedDRA classification system and reported in each DSMB communication both by MedDRA System Organ Class (SOC) and overall. Both the number of individuals with one or more of AEs within each SOC, as well as the total count of all AEs within each SOC, will be reported. These will be accompanied by point and 95% confidence interval estimates of the proportion of individuals who would experience AEs and the total count of AEs per person-time within each SOC, respectively. The latter computation will acknowledge clustering at the level of the participant by using generalized estimating equations (GEE) in estimation with robust variance estimates used for computing confidence intervals.

We will use variance decomposition to generate estimates of within and between-individual variation in functional outcomes that would potentially be used in a subsequent trial (see above), along with confidence interval estimates for said variance measures, in order to assist in planning of the subsequent study. We will also conduct an exploratory analysis of the mean change in these endpoints using mixed-effects linear regression of all time points, with a random effect included at the participant level in acknowledgement of serial correlation of repeated measures. Dependent variables will be the change in outcomes related to average daily activity from baseline to the six-week post-tDCS follow-up period, as well as the change in laboratory-based functional outcomes from baseline to each planned follow-up visit.

Feasibility outcomes:

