The proposed sample size was motivated by our experience in similar pilot studies, the need to develop a sufficiently detailed profile of the background population and convincing demonstration of the feasibility of our protocols, the anticipated drop-out rate, and the need to make resource and sample size estimations for the subsequent trial. We anticipate, based on prior work, that we will screen between 5 and 15 individuals for each participant enrolled. Enrollment of 32 individuals will allow us to determine within 1 individual the expected number of participants screened to enrolled in the subsequent trial using an 80% confidence interval; similarly, we will be able by the same method to estimate the probability a given participant will complete intervention to within 0.10.

Functional outcomes:

Assuming type-I error probability = 0.05 and cumulative attrition and missingness approximately = 20% (i.e.

evaluable data on 26 participants with complete data, the design will obtain 90% power to detect standardized differences [ratio of mean within-participant difference on endpoints to the standard deviation (SD) of same] of at least 0.41, and 80% power to detect effects of 0.36 or greater.

Our primary functional endpoint is habitual physical activity defined as average daily step counts derived from a FitBit wristband. As no prior study has investigated the change in total steps per week as a result of this type of intervention, we estimate the SD of the intervention-attributable change based on prior data on changes in weekly step counts in other conditions. Given that a prior study of pulmonary rehabilitation demonstrated a SD of 150 steps per week,⁸⁴ we will have 90% power to detect changes as small as 62 steps per week, and 80% power to detect 54 steps per week.

The GPS data will be analyzed by the team at the University of Pittsburgh. The GPS data were downloaded to a secure computer and saved with only the study ID number. Our team will upload the GPS data to the secure server at the University of Pittsburgh. No other identifiable information will be provided to the team at the University of Pittsburgh.

Data Storage and Confidentiality

Data Storage

All data collected for analysis will be de-identified and assigned a unique study number. Data collection forms will be kept in a locked file cabinet in the office of the PI at Hebrew SeniorLife. Data will be entered and stored on a password-protected secure server at HebrewSeniorLife.

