
Participants may not receive any significant health benefit from participation, although some may benefit from

knowledge of their health status, as well as potential therapeutic effects of completing a behavioral intervention to increase physical activity. Participants will be provided a \$160 stipend to help cover the costs of their time spent completing study procedures. They will also have the option to keep the Fitbit device that they use in the study.

We believe that the potential benefits of establishing tDCS as a noninvasive intervention to improve goal-directed physical activity in physical inactive older adults significantly outweigh the above-outlined potential risks to participants, which are expected to be minor, transient and relatively rare.

The observations from these studies are expected to provide important information regarding the effects of noninvasive electrical brain stimulation on goal-directed physical activity in older adults. Results are also expected to provide insights into the feasibility and effectiveness of such intervention within this population, thus increasing the potential for deployment of tDCS interventions to larger numbers of older adults.

Costs incurred during the study for medical care/injury

Any subject who suffers an adverse event during the conduct of study protocols will receive the medical care necessary to treat the adverse event. If we cannot provide the care directly, we will arrange for the medical care to be provided to the subject. If the event meets the definition of a serious adverse event, the participant will be removed from the study, and will be referred to their primary care physician for ongoing care. The treating provider will bill the insurance company or other third parties, if appropriate, for the care a participant receives for any injury. We will try to have these costs paid for, but the participant may be responsible for some of them. For example, they may be responsible for payment of any deductibles and co-payments required by the insurer. There are no plans to provide any compensation for an injury beyond what is described above, should one occur. If the event does not meet the criteria of a serious adverse event, and the participant is willing and able to continue, he/she will be able to continue and complete the study

Payment to Participants

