Describe the type remuneration and the timing of remuneration to study procedures e.g. participants will be provided with \$50 per study visit, to be distributed as visits are completed, etc.

Participants receive up to \$160 for taking part in this study. Participants will also receive a FitBit and will be able to keep it when the study has ended if they wish. Specifically, participants will receive the following amounts for each visit completed:

Visit 1 - In-person screening visit - \$10 Visit 2 – Baseline visit - \$10

Visits 3- 12: Brain stimulation – 10 visits over two weeks; \$10 for each visit= total of \$100

Visits 13-14: Follow-up assessment visits - \$10 for each visit = \$30 total for completion of all 3 follow-up visits.

Visit 15: Final in-person counseling session - \$10 Visit 16: Final follow-up study assessment - \$10

Participants will receive a check in the mail within eight weeks of study participation.

Participant Withdrawal

Participation may be terminated at the discretion of the PI, if the PI feels that study discontinuation is necessary to protect the participant, or that there are unmanageable factors which will interfere significantly with the study procedures and/or interpretation of results. The study participant will be informed of this and withdrawn from the study. The participant can, at any time, request the study be terminated and to be withdrawn. Any previously collected data prior to termination/withdrawal will be maintained in the study data set.

Adverse Event Reporting

An adverse event is any untoward medical occurrence in a participant, whether or not it is causally related to the study. An adverse event can therefore be any unfavorable and unintended sign (including an abnormal laboratory finding, for example), symptom or disease temporally associated with the study. Adverse events will be recorded on the appropriate case report forms and source documents. The investigator and/or trained staff member will evaluate all adverse events as to their severity and relation to the test article. The severity of adverse events will be graded as follows:

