Serious adverse events will be reported to the IRB, as well as the identified Safety Monitor, within 24hrs by fax or email. A related written report will be submitted within 5 business days of learning of the event, and a submission of the incident to the IRB system will be completed within one week of learning of the event. This form will record any adverse symptoms and/or study protocol deviations.

All other adverse events/study incidents will be reported to the HSL IRB and identified Safety Monitor, according to policy, within 5 business days of learning of the event. A related submission of the incident will be completed via the eIRB system within one week of learning of the event.

Safety Monitoring

Safety monitoring procedures will be implemented and reviewed by a Safety Monitor (to be determined upon Notice of Grant Award), in accordance with NIA safety policies for human intervention studies.

The criteria for discontinuing a participant's participation include the participant's request, as well as any unexpected life-threatening or potentially disabling event, including syncope, an injurious non-accidental fall, hemodynamic collapse, stroke, transient ischemic attack, dysrhythmia, renal insufficiency, angina, myocardial infarction, anaphylaxis, acute hemorrhage, or hospitalization for acute illness. These adverse events will be recorded in accordance with IRB requirements and included in the study database. If a determination about

continued participation cannot be made according to these criteria, the adverse event report will be faxed to the un-blinded Safety Monitor, who will make the final decision.

Prior to the start of the study the Safety Monitor will review the IRB approved protocol, procedure manual and informed consent documents, with regard to participant safety, recruitment, randomization, intervention, data management, quality control, and confidentiality. The Safety Monitor will recommend any necessary changes of the protocol to the PIs and will review and approve revisions. The Safety Monitor will identify relevant data parameters and the format of the information to be regularly reported.

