The Safety Monitor will then meet biannually with the investigators to review standardized reports. He/She will review the progress of recruitment and retention of participants, compliance with the protocol, and operating procedures. If they raise concerns about safety issues, they may request additional data and propose specific analyses. They will make recommendations to the PIs regarding recruitment, retention, compliance, and safety issues, and will

The investigator and/or trained staff member will evaluate all adverse events as to their severity and relation to the test article. The severity of adverse events will be graded as follows:

- Mild: Awareness of a sign or symptom but easily tolerated.
- Moderate: Discomfort sufficient to cause interference with usual activity or to affect clinical status.
- Severe: Incapacitating with inability to do usual activity or to significantly affect clinical status.
- Life Threatening: The participant was at immediate risk of death from the adverse event as it occurred.

The Investigator will also assess the relationship of any adverse event to study, based upon available information, using the following guidelines:

- 0 = Unlikely: No temporal association, or the cause of the event has been identified.
- 1 = Possible: Temporal association, but other etiologies are likely to be the cause; however, involvement of the study procedures cannot be excluded.
- 2 = Probable: Temporal association, other etiologies are possible, but not likely.

A serious adverse event is any experience that results in any of the following outcomes: death, is life threatening, inpatient hospitalization or prolongation of hospitalization, a persistent or significant disability/incapacity. Important medical events that may not result in death, be life-threatening, or require hospitalization may be considered a serious adverse event when, based upon appropriate medical judgment, they may jeopardize the patient or participant and may require medical or surgical intervention to prevent one of the outcomes listed in this definition.

Unanticipated and adverse event reporting

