The criteria for discontinuing a participant's participation include the participant's request, as well as any unexpected life-threatening or potentially disabling event, including syncope, an injurious non-accidental fall, hemodynamic collapse, stroke, transient ischemic attack, dysrhythmia, renal insufficiency, angina, myocardial infarction, anaphylaxis, acute hemorrhage, or hospitalization for acute illness. These adverse events will be recorded in accordance with IRB requirements and included in the study database. If a determination about continued participation cannot be made according to these criteria, the adverse event report will be faxed to the un-blinded Safety Monitor, who will make the final decision.

Publication Plan

We will register this clinical trial at ClinicalTrials.gov. We also will ensure that informed consent documents for this clinical trial will include a specific statement relating to posting of clinical trial information at ClinicalTrials.gov. Hebrew SeniorLife's Institute for Aging Research has an internal policy in place to ensure that clinical trials registration and results reporting occur in compliance with policy requirements. Results will be disseminated through publications in peer-reviewed medical journals, presentations at national meetings, and announcements on the HSL website and other public media.

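### Removing every participant with a serious adverse event from the study also ends step and functional follow-up; continuing it with consent would be a cheap improvement

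*Protocol*

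**What the plan says.** Four places in the protocol govern what happens after a serious event or a withdrawal.

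- **Costs incurred during the study for medical care/injury:** "If the event meets the definition of a serious adverse event, the participant will be removed from the study", with referral to primary care. The same paragraph lets a participant whose event is not serious carry on to the end if willing and able.
- **Participant Withdrawal:** termination by the investigator or at the participant's request is withdrawal from the study. On data, the section says only this: "Any previously collected data prior to termination/withdrawal will be maintained in the study data set".
- **Safety Monitoring:** "The criteria for discontinuing a participant's participation include the participant's request, as well as any unexpected life-threatening or potentially disabling event", followed by a list that includes stroke, injurious non-accidental fall and hospitalization for acute illness. Cases these criteria do not settle go to the un-blinded Safety Monitor.
- **Participant discontinuation:** the same criteria are repeated, opening with "The criteria for discontinuing a participant's participation include the participant's request".

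The definition of a serious event, given under Safety Monitoring, includes "inpatient hospitalization or prolongation of hospitalization, a persistent or significant disability/incapacity". It does not require a link to the study procedures.

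The SAP (Statistical Methods) analyses change in average daily steps from baseline to each two-week period. It has no rule for missing data, withdrawal or events that interrupt follow-up. The protocol's Data Analysis section plans to "generate estimates of within and between-individual variation in functional outcomes that would potentially be used in a subsequent trial", and its Feasibility outcomes section gives as one reason for the sample size "the need to make resource and sample size estimations for the subsequent trial".

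**The concern.** Stopping stimulation after a serious event protects the participant. Ending step recording adds no obvious protection, yet the protocol does both in one step. Read literally, a short unrelated admission in week 7, after all ten stimulation sessions are over, ends step follow-up.

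The periods lost are unlikely to be typical. A hospital stay, stroke or injurious fall probably reduces walking, so the missing values are probably among the lowest. A conventional repeated-measures ANOVA would drop participants with incomplete periods. The mixed model also named in the SAP would keep their earlier periods but assumes that data are missing at random.

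What is at stake is mainly the pilot's output for planning. Without low post-event values, mean step change may look too high and its variance too small, and a next trial sized on those figures could be too small. The tDCS-versus-sham contrast is biased only if events, or their effect on steps, differ by arm. The documents give no reason to expect that.

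A lesser point is that the removal rule and the two discontinuation lists word their criteria differently. The lists are not exhaustive, so the texts can mostly stand together and need only minor harmonisation.

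**Working it through.** **Reading the rules together.** The cost section contrasts serious events (removed) with non-serious ones (may continue and complete), so removal there means not completing the study. The two discontinuation sections end participation, not just stimulation. The withdrawal section addresses only data already collected. No section separates stopping the intervention from stopping follow-up, and none provides for FitBit, GPS or functional data after removal.

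**Inputs from the documents.** 32 enrolled, 16 per arm; "We have conservatively planned for approximately 20% attrition", leaving 26 complete datasets; eight weeks of follow-up analysed in two-week periods.

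**Assumptions.** The documents give neither a serious-event rate nor the effect of such an event on steps. I take 1%, 3%, 5% and 10% of participants over the eight weeks, and a step change 1 or 2 SD lower after an event.

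**The plan's own figure.** 32 × (1 − 0.20) = 25.6, rounded to 26, so it reproduces. The allowance is 32 − 26 = 6 people.

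**Expected removals.** With X ~ Binomial(32, p):

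| p | Expected, 32p | P(X ≥ 1) | P(X > 6) |
|---|---|---|---|
| 1% | 0.32 | 28% | 0.00000003 |
| 3% | 0.96 | 62% | 0.00004 |
| 5% | 1.6 | 81% | 0.0009 |
| 10% | 3.2 | 97% | 0.036 |

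The rule may well be used, but removals alone are unlikely to exhaust the allowance.

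**Participant-periods lost.** 8/2 = 4 periods each, so 32 × 4 = 128. If removal is equally likely in each period and that period is lost (assumption), the mean loss is (4 + 3 + 2 + 1)/4 = 2.5 periods per person removed. One to three removals lose 2.5 to 7.5 of 128, or 2.0% to 5.9%.

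**Distortion in the last period.** Let k of 32 be removed, q = k/32, with post-event change d SD lower, equal SD otherwise and no other attrition. Leaving these people out overstates mean change by q × d. The full variance is 1 + q(1 − q)d² against an observed variance of 1.

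| k | d | Mean overstated (SD) | Full variance | Observed/full | Variance understated |
|---|---|---|---|---|---|
| 1 | 1 | 0.031 | 1.030 | 0.971 | 3% |
| 1 | 2 | 0.063 | 1.121 | 0.892 | 11% |
| 3 | 1 | 0.094 | 1.085 | 0.922 | 8% |
| 3 | 2 | 0.188 | 1.340 | 0.746 | 25% |

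The last period is the worst case, because all removals have accumulated by then. With removals spread evenly, the average share missing over four periods is (1 + 2 + 3 + 4)/16 = 0.625 of q, so the average overstatement is 0.625 × 0.031 = 0.02 to 0.625 × 0.188 = 0.12 SD.

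**Precision.** The between-arm detectable effect at two-sided 0.05 and 80% power is (1.960 + 0.842) × √(4/N). It is 1.10 SD at N = 26 and 1.08, 1.06 and 1.04 SD at N = 27, 28 and 29. Keeping one to three people gains at most 0.06 SD.

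**The case against.** The strongest objection is that the plan never says data collection stops. The procedure manual is not supplied and consent pages are not part of the supplied text; rules on data after withdrawal often sit there. The removal sentence appears in a section about costs and billing, while the dedicated discontinuation sections are narrower and leave unclear cases to the Safety Monitor. The withdrawal section is not a serious-event rule, and keeping earlier data is good practice. This makes the reading an inference, though still the natural one: the removal sentence has no condition, and nothing supplied restores follow-up.

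A second objection concerns the estimand. The endpoint is habitual activity, which steps during a hospital stay arguably do not measure. If the next trial kept the same removal rule, variance without post-event data would be the relevant input. But collecting the data still permits an analysis restricted to time before the event, whereas not collecting them rules out the alternative.

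Third, the size rests on assumed rates and drops. The variance calculated is a cross-sectional one, not the within- and between-person components the protocol wants, and a hospitalised participant may not wear the device. All of this stands and keeps the point small.

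Fourth, the FitBit is also part of the behavioural intervention, so continued wear leaves some of that in place. The follow-up visits include fast and dual-task walking, a real burden after a stroke or infarction. The planned optional tracking is offered only at Visit 18, so it shows that such tracking is feasible but does not cover people removed earlier. These points argue for medical clearance and a FitBit-only option, not for ending all follow-up.

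**Conclusion.** The concern holds as a minor improvement to the design. Followed as written, the protocol loses step and functional outcomes after events that probably lower them. Under the assumed rates, roughly zero to three of 32 participants are affected. The upper end of the distortion needs three removals and a 2 SD drop; one removal with a 1 SD drop gives only 0.03 SD in the mean and 3% in the variance. The attrition allowance very probably absorbs the numbers lost, and the gain in precision is slight. The reason to change is to avoid outcome-related missing data in a pilot meant to inform the next trial. Confidence is medium, because the rule's effect on data collection is inferred and its size depends on figures the documents do not give.

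**What to change.** Put one rule in the four protocol sections named above. A serious adverse event as defined under Safety Monitoring, or an event on the discontinuation list, stops any remaining stimulation and, where needed, counselling and the step goal. It does not by itself end outcome collection.

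- With the participant's agreement, continue FitBit and GPS recording.
- Hold the follow-up assessments only when medically cleared, with FitBit-only follow-up as the lighter option.
- Leave undecided cases with the Safety Monitor and keep full withdrawal open at any time.
- Analyse participants in their assigned arm, and report intervention discontinuation separately from loss to follow-up.

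This does not restore session or intervention completion and is not meant to.

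The cost is a change to protocol and consent wording, plus modest burden for perhaps zero to three people: wearing, charging and syncing the FitBit (staff sync in person for those without a computer or smartphone), carrying the GPS device, and the remaining 1.5-hour assessments. No new equipment is needed: staff already monitor uploads through the company's website, and participants may keep the FitBit. Enrolment stays at 32.
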